Although health promotion related to weight, diet, smoking, alcohol intake and physical activity is part of the usual rehabilitation in CSCI, a systematic approach, follow up and feedback is not provided. Assessment of metabolic profile, body composition and physical capacity is not part of the usual care. In the masterplan for patient care at CSCI, health promoting initiatives are described as "communication and conversation with a health promoting purpose with the patient on a daily basis". How the communication is carried out in practice, and whether some health care professionals have a particular responsibility or expertise related to certain aspects of health promotion eg. based on tests or assessments of health, is unclear and not described in detail. A well described and systematic approach related to health care promotion may ensure that all patients at CSCI receive information and knowledge related to health promotion and the risk of cardiovascular disease.

Sub projects

The project consists of a prospective national survey in collaboration with Spinal Cord Injury Centre of Western Denmark and an intervention at CSCI (see the timeline), which results in 4 sub projects

Sub project 1. Prospective representative national survey of Body Mass Index.

This study includes all patients with a new SCI hospitalized at CSCI or Spinal Cord Injury Center of Western Denmark during a period of 9 months whereby 100 patients are expected to participate. On the basis of usual rehabilitation today, data concerning BMI, level of functioning (SCIM III) and neurological status (ISNCSCI) are collected at admission and discharge. At CSCI BMI is collected every 6 weeks. Also the data for quality of life (QoL SCI), depression (PHQ-2), PA (LTPAQ-SCI) and self-assessed ability to be physically active (ESES) will be collected during this period and at follow up 6 months after discharge. A VO₂peak test at discharge is performed and in some patients measurements of accelerometry (AH) will be performed. Patients with a new SCI who are admitted for rehabilitation several months after the time of injury are also included in the prospective survey. Therefore the data for BMI at the time of injury is collected for all patients at admission to primary rehabilitation from both the patient journal and also by asking the patient about weight and height at the time of injury. Data from this subproject serves as a historic control in the Ph.D project.

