Pre-intervention education of health care professionals and mentors: Before onset of the intervention, all health care professionals and mentors with a SCI at CSCI will receive information and education about the content and elements of the intervention, cardiovascular risk factors in people with SCI and the effect of PA and healthy diet in order to establish a uniform knowledge at a basic level among all health care professionals and mentors at CSCI as called for in the literature [9]. The sessions are supplemented with evidence based recommendations that can be used by the health care professionals and mentors when they educate the patients. The review by Van Wyk et al emphasizes that patient education is an important part of the interdisciplinary rehabilitation of people with SCI and recommend an individualized approach and the use of different settings in which the patient can receive the education.

Therefore the intervention will include an increased focus on cardiovascular risk factors and systematization of the existing setting and treatment interventions including education of patients- and their relatives in different in different types of forums [45, 46]. New interventions are introduced and several of the outcome measures at admission, discharge and follow up 6 months after discharge are a part of the intervention to facilitate PA and healthy diet through strategic patient education including body weight, body composition, metabolic profile, physical capacity, physical activity, self- assessed ability to be physically active and diet. Also included are instruction and information about PA and the intensity of this by using ratings of perceived exertion, identification of activity and participation problems related to PA and healthy diet using the Canadian Occupational Performance Measure, information about the recommended amount and composition of food on a plate at the lunch and evening servings but also in conjunction with kitchen training and grocery shopping with the occupational therapists. A motivational conversation, tools for decision making, and use of mentors with SCI to facilitate PA and healthy diet are also introduced.

Patient adherence to the elements of the intervention is described descriptively by registration of their participation in the different elements in which they are expected to participate. The adherence of the interdisciplinary health care professionals in relation to the intervention is

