This study includes a subsample of 20 patients participating in subproject 1. The equipment used for monitoring amount and intensity of PA consists of sensors registering acceleration and heart rate and is placed on the thorax of the participant with two surface electrodes. The equipment has previously been used in wheelchair dependent people with SCI, although the reliability of the equipment has not previously been assessed [35]. The precision of the equipment is higher when calibrated individually to the participant using an exercise test [68]. In this project individual calibration will be made during the exercise test described in subproject 3, and continuous measurements of amount and intensity of PA will be made during a period of 24 hours. The test-retest is performed at discharge, separated by 48 hours or within maximum 5 days at the same time of the day.

Outcome measures

All outcome measures will be collected at admission, discharge and follow-up 6 months after discharge. At CSC data for BMI is also collected every 6th week during the hospitalization period.

Primary outcome

Oxygen uptake: Is measured as VO₂peak during a maximal exercise test and is gold standard for measuring aerobic capacity. For people with a SCI several test protocols have been used [36]. The test in this project is performed by using the integrated test protocol in the software of NuStep XR5 or SCI FIT Pro 1. Gradual increments in workload is added every minute depending on the level of lesion. The participant maintains a fixed cadence until predefined criteria for VO₂peak is reached after 8-12 minutes. If VO₂peak is not reached during this period the workload increases each minute until VO₂peak [36, 67]

Secondary outcomes

Objective physical activity: Is measured in a sub-sample in the historic control cohort and the participants in the intervention study with a multisensor device (Actiheart®) recording accelerations and heart rate. It is previously used for wheelchair users with a SCI and individual calibration is important to get the most accurate data [29].

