Self - reported physical activity: Is measured by the Leisure Time Physical Activity Questionnaire for people with Spinal Cord Injury (LTPAQ-SCI) which is a self- administered questionnaire concerning leisure time PA, including amount and intensity the past 7 days. LTPAQ-SCI uses a scale for perceived exertion which is validated against VO₂-peak and the Borg-scale. Reliability and validity of the self- reported activity level is satisfactory in the moderate and high intensity area [13]. For people hospitalized during primary rehabilitation, defining leisure time may be difficult. Therefore an instruction defining leisure time in this context was formulated describing leisure time PA as being PA that is not part of the patients weekly schedule, is not planned together with the health care professionals as part of the rehabilitation and is not self- administered exercise which is planned or scheduled as part of the rehabilitation. Therefore leisure time PA is any kind of spontaneous PA that is not planned or schedule together with a physiotherapist or other health care professionals. This kind of necessary PA is described in the additional question developed for the study. The question will be designed as the original questions and the same intensity scale is used.

Self- assessed ability to be physically active: Is measured by the Exercise Self Efficacy Scale for people with Spinal Cord Injury (ESES) which is an outcome measure developed for assessing self- efficacy related to PA in people with SCI, and consists of 10 questions which are answered on a 0-4 scale. ESES is reliable with a high internal consistency (Cronbach's alpha 0,94). Also content validity in the form of face and construct validity are satisfactory [41].

Measure of patient participation /shared decision making

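### Teaching patients to gauge activity by perceived exertion may change how they answer LTPAQ-SCI, so its intensity results can move without a change in activity

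*Protocol*

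**What the plan says.** **The programme.** The section on sub project 2 describes what is included in the intervention. One item is "instruction and information about PA and the intensity of this by using ratings of perceived exertion". The same section makes several outcome measures, physical activity among them, part of the patient education, with feedback to the patient.

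**The outcome.** Under Outcome measures, self-reported physical activity is a secondary outcome measured by LTPAQ-SCI, a "self- administered questionnaire concerning leisure time PA, including amount and intensity the past 7 days". On how intensity is graded, the text says "LTPAQ-SCI uses a scale for perceived exertion". For the extra question on activity planned as part of rehabilitation, it says "The question will be designed as the original questions and the same intensity scale is used". On measurement quality it says "Reliability and validity of the self- reported activity level is satisfactory in the moderate and high intensity area".

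**Timing and comparison.** "All outcome measures will be collected at admission, discharge and follow-up 6 months after discharge". The footnote to the table in sub project 2 places the admission measurements 1-2 weeks after admission. Of sub project 1, which runs under usual rehabilitation and also collects LTPAQ-SCI, the protocol says "Data from this subproject serves as a historic control in the Ph.D project". The Statistics section reports change over time by paired t-test.

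**The concern.** A before-after comparison of a self-rated quantity assumes that patients use the rating scale in the same way on each occasion. Here an element of the treatment is instruction in judging intensity by exertion, and the outcome asks patients to grade intensity by exertion. A patient who has learned to recognise moderate effort may place the same activity in a different band at discharge than at admission.

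The description of usual rehabilitation does not list such teaching, so the same possibility enters the contrast with the historic controls. Maintenance of physical activity after discharge is part of the study hypothesis, and the moderate and high range is the part of LTPAQ-SCI for which the protocol claims satisfactory properties. An intensity result from that range could be reported as changed behaviour when part of it is changed rating.

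**Working it through.** The protocol gives no figure to reproduce: it has no power calculation, no LTPAQ-SCI mean or SD, and no expected effect. The check is a reading of the text, followed by two illustrations on assumed inputs.

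**Step 1: the passages side by side.**
- Treatment: instruction on intensity through exertion ratings (sub project 2).
- Outcome: intensity graded by perceived exertion, in LTPAQ-SCI and in the added question (Outcome measures).
- Order: discharge and 6-month answers come after teaching given during the stay. The admission answer comes 1-2 weeks after admission, and the start of the teaching is not stated.
- Controls: usual rehabilitation, with no exertion teaching listed.
- Safeguard: the quoted validation ("LTPAQ-SCI uses a scale for perceived exertion which is validated against" VO2peak and the Borg scale) does not address a change in how the scale is used after instruction. Actiheart is listed as a separate outcome, and the text does not tie it to the interpretation of LTPAQ-SCI.

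It follows that intensity results can mix activity with rating habit. It does not follow that they will, or in which direction.

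**Step 2: re-rating with activity unchanged.** Assumed start: 100 mild and 60 moderate-or-heavier minutes a week, total 160. These minutes and band labels are chosen for illustration. If a share r of mild minutes is re-rated upward, moderate-or-heavier minutes = 60 + 100r, and the relative rise = 100r / 60.
- r = 10%: 70 minutes, 10/60 = 17%.
- r = 20%: 80 minutes, 20/60 = 33%.
- r = 30%: 90 minutes, 30/60 = 50%.

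The total is 160 throughout. Re-rating downward lowers the moderate-or-heavier minutes at the same fixed total and could hide a real gain.

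**Step 3: would a paired t-test notice?** Suppose re-rating alone moves the mean paired difference by d standard deviations of the differences. The two-sided 5% rejection probability comes from the noncentral t distribution with n − 1 degrees of freedom and noncentrality d√n. The Statistics section expects about 40-60 patients in the intervention study (sub project 2 gives 50-60 complete data sets).

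| n | d = 0.2 | d = 0.3 | d = 0.4 | d = 0.5 |
|---|---|---|---|---|
| 40 | 0.24 | 0.46 | 0.69 | 0.87 |
| 50 | 0.28 | 0.55 | 0.79 | 0.93 |
| 60 | 0.33 | 0.63 | 0.86 | 0.97 |

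The values of d are assumptions. The table shows only that a modest rating shift, if it occurred, could be declared significant at this sample size.

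**Step 4: a rise in total minutes is no check.** Suppose true activity rises by 10 mild minutes, to 110 mild and 60 moderate-or-heavier (total 170), and 20% of mild minutes are re-rated. The moderate-or-heavier figure becomes 60 + 22 = 82. Total and intensity both go up, yet no minute was more intense than before.

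**The case against.** The strongest reply is that the protocol does not show any shift. It names neither the scale used in the teaching nor its amount or timing. The teaching may simply use exertion to explain training intensity, and LTPAQ-SCI has its own scale. Some programme patients may already have met the teaching when they complete the admission questionnaire. Usual rehabilitation includes cardiovascular exercise, and the protocol itself says its health-promotion talk is not described in detail, so controls may also have met exertion ratings. No moderate-or-heavier endpoint is fixed, total amount is collected anyway, and the choice of LTPAQ-SCI summary can properly be left to an analysis plan. Actiheart is planned for the intervention participants.

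Most of this stands, and it limits the claim. A reader might infer that programme patients answer on a re-learned scale while controls and admission answers are untaught, and that the activity result is therefore biased. The documents do not support that. They show that exertion teaching belongs to the programme and is not listed in usual care, but they do not document what controls or newly admitted patients had been told, or that the two scales are the same.

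What remains is that nothing in the text keeps the rating task equal across occasions and cohorts. Actiheart is only a partial answer: it covers a sub-sample of the controls (sub project 4 gives 20 patients, monitored for 24 hours), and the protocol does not link it to LTPAQ-SCI. How the questionnaire is introduced belongs to data collection, and an analysis plan cannot repair it afterwards.

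**Conclusion.** The point holds as a caution. Intensity ratings from LTPAQ-SCI and the added question may shift after the programme's exertion teaching, relative to admission and to the historic controls, without a change in activity. Direction and size are unknown. The 17% to 50% and the rejection probabilities rest wholly on assumed inputs and are not estimates for this study.

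The reach is narrow. Re-rating between bands leaves total leisure-time activity unchanged, and VO2peak is not affected by this mechanism. It would be wrong to read this as undermining the study's main result, or as evidence that an activity gain will be exaggerated, since re-rating could equally hide one. It is a minor improvement, worth making because it is cheap and because ratings already collected cannot be put on a common footing later.

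**What to change.** 1. The protocol already plans a study-written instruction defining leisure time for LTPAQ-SCI. Extend it with one short explanation of the exertion scale, identical at every administration in both cohorts.
2. Have the sub project 2 admission questionnaire completed before exertion teaching starts.
3. Name the total LTPAQ-SCI amount as the main self-report result. Describe a change in the intensity bands as a change in activity intensity only where Actiheart supports it (sub project 2 participants and the control sub-sample). Otherwise report it as self-rated intensity that the teaching may have affected. Do not accept a rise in total minutes as confirmation.

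This is best settled before the controls are collected. The cost is a few lines of text and some attention to the order of events at admission. There are three downsides. Controls receive a brief scale explanation, which is a very small exposure. The sheet reduces but does not remove an imbalance that comes from face-to-face teaching. A true move from mild to moderate activity in patients without accelerometry would be reported cautiously.

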Study protocol Version: 1.0 date:04.12.17

Health promotion and cardiovascular risk reduction among people with spinal cord injury:
physical activity, healthy diet and maintenance after discharge.

(Sub study 1: Prospective Survey of Body Mass Index in People With Spinal Cord Injury)

Health promotion and cardiovascular risk reduction among people with spinal cord injury: physical activity, healthy diet and maintenance after discharge.

Background The incidence of a Spinal Cord Injury in Denmark is 10-15/mill. annually [1]. It is a life changing event that affects all bodily functions below the level of lesion with significant costs for the individual and society, and with consequences that predispose to cardiovascular risk factors such as dyslipidemia, vascular inflammation, insulin resistance, diabetes mellitus type 2, hypertension and overweight. Likewise abdominal adiposity is an independent risk factor for diseases associated with the metabolic syndrome [2]. Cardiovascular disease is one of the most frequent causes of death among people with SCI and occur among 46% of those who have lived for 30 years or more with a SCI, and 35% of people with a SCI who are 65 years or older [3]. The cardiovascular risk factor, including consequences of an inactive lifestyle and weight gain during and after the primary rehabilitation, defines the primary focus of the current project.

The course of overweight

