Measure for a varied and healthy diet in an appropriate amount	Questionnaire	Ph.D student	-	X

*1-2 weeks after admission and before discharge Follow up approx. 6 months after discharge.

** Is handled by physiotherapists with knowledge and skills after the project.

Is handled by the Ph.D student at discharge and admission for depression and quality of life respectively.

Subproject 3. Test- retest reliability of a VO2 peak test

This study includes all patients participating in subproject 1 who are able of performing the test. A seated cross-trainer is used (NuStep T5XR) with an incorporated test protocol in the equipment software. Equipment and protocol is reliable in people with traumatic brain injury and has been validated in healthy persons [32, 33]. In people with an incomplete SCI the equipment is safe, and involves a large amount of muscle mass ensuring completion of the test [34]. The equipment may also be used by patients with a complete SCI of the lower extremities, but in case the equipment is difficult to use for people with a complete tetraplegia, an armcranking ergometer will be used (SCI FIT Pro1). The reliability of the cross-trainer has not previously been evaluated in people with SCI. The test- retest study takes place at discharge, separated by 48 hours or within maximum 5 days at the same time of the day. The participants refrain from caffeine, alcohol and intensive physical exercise on the day of testing as well as tobacco smoking to hours before the test. Bladder emptying is taken care off before the test.

Subproject 4. Test-retest reliability of a multi sensor accelerometer.

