Bodyweight: Is measured as Body Mass Index (BMI) which is the most widely used outcome measure for measuring bodyweight in people with SCI. BMI is not sensitive enough to distinguish between fat mass and lean body mass nor overweight in people with SCI. Lowering the cut-off for overweight to 25kg/m² the sensitivity increases although this adjustment is not used consequently in the literature [30]. BMI is already collected as part of the existing routines every week and data for BMI every 6th week until discharge will be included in the project. Some newly injured are admitted to primary rehabilitation several months after the time of injury, and the course of bodyweight may already have changed significantly since the time of injury. Therefore BMI at the time of injury is collected from the patient journal from the initial hospitalization during the acute stage and by asking the patient at admission to primary rehabilitation about the height and weight at the time of injury.

Body composition: Is determined by Dual energy x-ray absorptiometry (Dexa) which is gold standard for assessing obesity and body composition although cut-off values for people with SCI has not been established [30].

Metabolic profile: Consists of CRP as a marker for inflammation, BP, Lipid profile: Total cholesterol, Triglycerides, HDL cholesterol, LDL cholesterol which all are included in the International SCI Endocrine and Metabolic Function Basic Data Set, as well as Hemoglobin A1c as

a marker for carbohydrate metabolism, and is included in the International SCI Endocrine and Metabolic Extended Data Set [31, 32].

Level of functioning: Is determined by the Spinal Cord Injury Independence Measure III (SCIM III) which is a valid and reliable outcome measure designed to assess level of functioning in people with SCI in a clinical setting and in research [33] [34, 35]. The SCIM is composed of 19 items that assess 3 domains. 1 Self-care (6 items, scores range from 0-20). 2 Respiration and sphincter management (4 items, scores range from 0-40). 3 Mobility (9 items, scores range from 0-40). The total SCIM scores range from 0 to 100. SCIM III is already collected as part of the existing routines at CSCI.

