Data from the patient journals in Epic and the different outcome measures used, is stored in a web based database (Redcap) which is created by the regional Centre for IT, Medico and Telephony (CIMT), with limited access and ID- code, to which pseudo anonymized data is transferred directly,

or via an encrypted USB-stick. An identification list is stored in a locked cabinet at CSCI, local 3403.

Data is stored until December 31, 2027 after which paper material is shredded and data files are deleted.

Statistics

The intervention study and follow up is performed as a pragmatic study and includes, with a few exceptions, all newly injured patients with SCI admitted to primary highly specialized rehabilitation at CSCI. Patients will be included during a time period of 18 corresponding to approximately 40 – 60 patients. Due to the rareness of the morbidity a power calculation is not performed for the primary outcome prior to the intervention, but it is assumed that the total participant number in the intervention and in the historic control cohort, will be comparable to the existing scientific literature.

Numeric continuous data collected at admission, discharge and follow up is reported descriptively as mean and standard deviation together with 95% confidence intervals, or as median, upper and lower quartile as well as interquartile range. Changes over time is reported on the basis of paired t-test. In subproject 3 and 4 the reliability of the outcome measures is analyzed by paired t-test, Pearsons product moment correlation and coefficient of variation or Intraclass correlation coefficient between the test- retest sessions.

Participants, inclusion- and exclusion criteria

Inclusion criteria: All newly injured patients within the previous 12 months, with a SCI and admitted at CSCI are included, regardless of age, neurological level of lesion and completeness of the injury. In subproject 1 all newly injured people with SCI admitted at VCR are also included. Patients under the age of 18 will participate if informed consent is retrieved from their parents.

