Exclusion criteria: Insufficient skills in Danish language and reduced mental function that prevents reading and answering the questionnaires. For the VO₂peak test: Motor complete SCI (AIS A and B) at C4 level or above and assisted ventilatory function. Other exclusion criteria are the presence of decubitus, severe spasticity or musculoskeletal problems considered at risk of aggravation during testing or preventing completion of the test.

Recruitment of participants:

All newly injured patients who are admitted for rehabilitation at CSCI during the project period are included in the intervention (subproject 2) as it becomes a part of usual care during the project period. The Ph.D student is informed about new and future admissions at CSCI by local patient lists every week, and LTPAQ-SCI, ESES, QoL_SCI and NORMON is handed out to the patient and collected again by the Ph.D student. Date and time for the VO₂peak test is handed to the patients physiotherapist, who will make sure to enter it into the patients weekly schedule. The same procedure is repeated at discharge except that QoL_SCI is collected as a part of existing procedures and PHQ-2 is collected by the Ph.D student. In subproject 1, data for VO₂peak at CSCI will only be collected at discharge. All newly injured patients who are admitted for rehabilitation at VCR in the same period are recruited for subproject 1 and data for BMI, SCIM III and ISNCSCI is collected as a part of existing procedures in usual care.

The coordination related to booking of the DEXA-scan and transportation for this is managed by the secretaries. Ordination of the DEXA-scan as well as blood samples related to metabolic profile is handled by the doctors.

Ethical considerations

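### CRP is a change outcome, but nothing is recorded at the blood draw to separate acute illness from low-grade inflammation, so resolving illness could appear as reduced cardiovascular risk

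*Protocol*

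**What the plan says.** Under Outcome measures, the Metabolic profile entry is a secondary outcome that "Consists of CRP as a marker for inflammation, BP, Lipid profile" and HbA1c. The Background lists "cardiovascular risk factors such as dyslipidemia, vascular inflammation, insulin resistance, diabetes mellitus type 2, hypertension and overweight" as consequences of the injury, and the Hypothesis expects the intervention to lower cardiovascular risk factors.

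On timing, Outcome measures states: "All outcome measures will be collected at admission, discharge and follow-up 6 months after discharge". The footnote to the intervention table places the inpatient measurements "1-2 weeks after admission and before discharge", with follow-up at about six months. The inclusion criteria admit all patients injured within the previous 12 months.

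On the conditions of sampling, the Recruitment section says only that ordering "blood samples related to metabolic profile is handled by the doctors". Pressure ulcers do appear in the exclusion criteria ("Other exclusion criteria are the presence of decubitus, severe spasticity or musculoskeletal problems"), but that sentence follows the VO2peak criteria and concerns problems that testing could aggravate or that would prevent its completion. It does not govern the blood samples.

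On analysis, the Statistics section says: "Changes over time is reported on the basis of paired t-test". Sub project 2 is a pre-post study. The data listed for Sub project 1, the historic control, do not include the metabolic profile, and the section on usual rehabilitation says that this profile is not part of usual care.

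**The concern.** CRP is an acute-phase protein. Infection, a pressure ulcer or recent surgery can raise it far above the low-grade range that matters for cardiovascular risk. The patients are newly injured inpatients, in whom such illness is plausible at any draw. The protocol anticipates pressure ulcers for the exercise test, sets preparation rules for that test, and collects a time-of-injury BMI because admission weight may already have shifted. CRP has no comparable safeguard.

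At stake is the reading of one component of a secondary outcome. A within-patient fall in CRP would agree with the hypothesis and could be reported as less vascular inflammation when it reflects recovery from illness. Even without a shift in the mean, a few very high values would hide a low-grade change.

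**Working it through.** The protocol gives no CRP level, standard deviation, illness frequency or power calculation, so there is no stated figure to reproduce. The calculation below is an illustration.

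**From the protocol.** Sub project 2 expects 50-60 complete data sets; the Statistics section gives 40-60 patients. The test is a paired t-test.

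**Assumed.** There is no true change. Background CRP is log-normal with median 3 mg/L, log SD 0.8 and correlation 0.6 between visits. A patient who is ill at the draw has an added log-normal amount with median 30 mg/L and log SD 0.7. The share ill is p1 at admission and p2 later, independently.

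**Step 1, mean shift.**
- Mean added amount = 30 × exp(0.7²/2) = 38.3 mg/L.
- Expected change = (p2 − p1) × 38.3.
- 10% vs 5%: −0.05 × 38.3 = −1.9 mg/L.
- 20% vs 5%: −0.15 × 38.3 = −5.7 mg/L.
- 30% vs 5%: −0.25 × 38.3 = −9.6 mg/L.
- 20% vs 20%: 0.
- 5% vs 20%: +5.7 mg/L.
- For scale, the background mean is 3 × exp(0.8²/2) = 4.1 mg/L.

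**Step 2, precision.**
- Variance of the background paired change = 2 × 9 × exp(0.64) × [exp(0.64) − exp(0.384)] = 14.6, so SD = 3.8 mg/L.
- The second moment of the added amount is 900 × exp(0.98) = 2398. Each visit with share p adds p × 2398 − (p × 38.3)².
- At p = 20% this is 479.6 − 58.8 = 420.8. With equal 20% shares the total is 14.6 + 2 × 420.8 = 856, so SD = 29.3 mg/L.
- At n = 50 the standard error rises from 3.8/√50 = 0.54 to 29.3/√50 = 4.1 mg/L, nearly eightfold, although the mean is unbiased.

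**Step 3, chance of a significant fall with no true change** (simulation, 4,000 runs, two-sided 5% test):

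| Share ill, admission vs later | Raw scale, n = 40 / 50 / 60 | Log scale, n = 40 / 50 / 60 |
|---|---|---|
| 0% vs 0% | 2.3% / 2.4% / 2.3% | 2.3% / 2.9% / 2.7% |
| 20% vs 20% | 2.1% / 2.2% / 2.5% | 2.4% / 2.2% / 2.8% |
| 10% vs 5% | 7% / 10% / 12% | 8% / 10% / 12% |
| 20% vs 5% | 37% / 45% / 53% | 38% / 46% / 54% |
| 30% vs 5% | 71% / 78% / 85% | 74% / 83% / 91% |
| 5% vs 20% | 0% / 0% / 0% | 0% / 0% / 0% |

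The log scale does not remove the false falls. Only the 0% vs 0% row corresponds to setting the affected samples aside.

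**Step 4, a second set of assumptions.** Let illness add a mean of 40-80 mg/L, in 10-25% of admission samples and 3-10% of later ones.
- Lowest: (0.10 − 0.03) × 40 = 2.8 mg/L fall.
- Highest: (0.25 − 0.10) × 80 = 12 mg/L fall (12.1 when simulated).
- With paired-change SDs of about 18 and 54 mg/L and n = 50, t is about 2.8/(18/√50) = 1.1 and 12.1/(54/√50) = 1.6. Both are below the critical value of about 2.01, so a typical trial here would show a noisy, non-significant fall.

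**Step 5, pairs kept by a restricted analysis.** The fraction is (1 − p1)(1 − p2). At 20% vs 5% it is 0.80 × 0.95 = 0.76, or 38 of 50 pairs. At 30% vs 5% it is 0.70 × 0.95 = 0.665, or about 33 of 50.

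**The case against.** A reader might infer that recovery from acute illness will show up as reduced vascular risk. The documents do not support that. The direction needs more illness at the admission sample than later, and no frequencies are given. Admission here means admission to rehabilitation, after an initial acute stay; sampling follows one to two weeks later, and some patients arrive months after injury. An infection at discharge or follow-up would push the change the other way. Even where the assumed direction holds, the second set of assumptions gives t of only about 1.1 to 1.6 at 50 pairs. This objection stands, and the point is therefore stated as conditional.

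A reader might also infer that a control cohort would not help. For the mean bias that is wrong: a comparable control sampled on the same schedule would show the same natural change, and the difference would cancel it. Only the added variance would remain. The protocol lists no such CRP series, however.

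Three further objections stand in part. First, the Statistics section allows median and quartiles as a descriptive summary, so it is not true that every value must enter a mean; the paired t-test for change remains. Second, scale and exclusion rules could sit in a statistical analysis plan that is not shown. Illness status at the draw is data collection, though, and belongs in the protocol. Patient journals are a study data source and might recover some of it, but less reliably for the draw after discharge. Third, the stakes are limited: VO2peak is primary, CRP is one component of a secondary outcome, and the entry calls it only a marker for inflammation. The vascular reading comes from joining that entry to the Background and the Hypothesis.

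**Conclusion.** The point holds in conditional form. As written, the plan mixes acute-phase values into the CRP result, keeps no record by which to separate them, and has no listed control series to show the natural course. The consequence depends on how illness is spread over the visits: an apparent fall if it is more common at admission, lost precision without mean bias if it is equally common, and an apparent rise if it is less common.

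Under the assumed inputs the chance of a falsely significant fall runs from the nominal 2.5% or so (equal shares) to 7-12% (10% vs 5%), 37-53% (20% vs 5%) and 71-85% (30% vs 5%) on the raw scale for 40 to 60 patients. All illness shares and CRP levels are assumptions, so these figures show sensitivity and do not predict the result. This is a cheap and worthwhile improvement to a secondary outcome. It does not affect the primary outcome or the data listed for Sub project 1.

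**What to change.** In the Metabolic profile entry, add that at each blood draw staff record whether the patient has a current infection, a pressure ulcer or recent surgery. This is the essential step, since the log scale alone leaves the bias in place.

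Then state that change in CRP is analysed on the log scale, that the cardiovascular CRP analysis is restricted to pairs without these conditions at either draw, that an all-values analysis is shown beside it, and that the number set aside is reported for each visit. Use any cut-off on the CRP value itself only as a pre-stated sensitivity analysis, because dropping values by their own level selects on the outcome.

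The cost is a short checklist and fewer paired values (about 12 of 50 at the assumed 20% and 5% shares). No extra procedure is needed, and usual care already assesses skin, bladder and respiration continuously. The restricted result describes only patients free of these conditions at both draws. It does not replace a control, so any natural course of low-grade inflammation stays in the pre-post change and should be acknowledged when CRP is reported.
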